8.6.2.3 PFS6

Proportion with PFS at 6 months (%PFS6) %PFS6 will be a key secondary endpoint for the overall study. With H_0 %PFS6 of approximately 20% (Section 4.3.6.2) and H_1 %PFS6 of 40% if n=40 are evaluable for PFS6, the power is 78% for 2-sided 5% alpha, or 87% with 1-sided 5% alpha using Fisher's Exact tests.

8.6.2.4 Median DOR, PFS, and OS

Median DOR will be summarized overall and according to anatomic subtype. Kaplan-Meier medians and quartiles may be provided if data warrant. Median PFS and OS will be summarized overall and according to anatomic subtype. If data warrant, Kaplan-Meier quartile estimates along with the 95% CI will be calculated. Descriptive summaries, including swim lane plots, may also be generated depending on results.

8.6.2.5 Re-Induction and Second Course Endpoints

Re-induction and Second Course outcomes for PFS, ORR, DOR, and OS will be measured as defined in Section 8.3.

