approximately 6-12 months (corresponding to Cycle 8-16) after enrollment (after the primary endpoint of PFS6 has been ascertained for that patient) (see Section 7.1.5.1). Repeat GM-CSF induction requires approval on a case-by-case basis from the Study Chair. Re-induction (r) PFS (rPFS and rPFS6) and response rate (rRR) will be described in these cases.

If ≥ 5 patients (approx. 20%) undergo GM-CSF re-induction and demonstrate restored CR or PR within 6 months after re-induction, the study team will consider whether to amend the protocol to allow for prolonged GM-CSF treatment or serial re-induction depending on the observed outcomes.

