7.1.5 Other Procedures

7.1.5.1 Re-Induction with GM-CSF

In patients who demonstrate CR, PR, or prolonged stable disease \geq 6 months with evidence of clinical benefit (such as minor response radiographically, decline in CA 19-9, and/or improved symptoms) after the Induction Phase but within 12 months from enrollment, but who subsequently progress on single-agent pembrolizumab between 6-12 months after enrollment (after the primary endpoint of PFS6 has been ascertained for that patient), re-induction with GM-CSF may be administered in case-by-case situations with approval from Study Chair provided patient remains eligible for ongoing treatment on protocol (section 7.1.5.3).

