8.3 Definition of Study Endpoints

8.3.1 Primary Endpoint

The primary endpoint was amended to be overall response rate (**ORR**) with addition of Expansion Cohort, based upon the promising responses observed during Stages 1 and 2 (Safety and Efficacy Cohorts). **ORR** is defined as the proportion of subjects with RECIST 1.1-measurable disease at study entry who have a complete response (CR) or partial response (PR) (confirmed + unconfirmed) using RECIST 1.1¹ at any time during the main study. Measurable disease has been added as a required inclusion criterion for Expansion Cohort eligibility. Re-induction and Second Course ORR (rORR, sORR) will be determined based upon response after first dose of re-induction or first dose of Second Course. Subjects with measurable disease at study entry who have unknown or missing response information will be treated as non-responders. Subjects with non-measurable disease at study entry will be excluded from ORR and DOR analyses.

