8.3.2 Secondary Endpoints

- 1) **Safety** endpoint assessment is described in Section 7.2. The safety endpoints are AEs graded using CTCAE (Version 4.0) criteria. Safety will be assessed by quantifying the toxicities and grades experienced by subjects who have received pembrolizumab plus GM-CSF induction, including SAEs and ECIs. Other safety endpoints include laboratory safety assessments, ECOG performance status, Child Pugh score, vital signs, and physical examinations. The incidence and frequency of dose reduction, treatment delays, and discontinuation for lack of tolerability will be quantified. Re-induction and Second Course safety events will be addressed in the same manner.

- 2) **Tumor PD-L1 status** will be measured by IHC and classified as positive or negative by central laboratory testing (QualTek Laboratories) using pre-specified cut-points.
- 3) A key secondary endpoint is %PFS6 (formerly primary endpoint, changed by amendment with addition of Expansion Cohort). For each patient, PFS will be calculated in days and months from date of first dose of protocol therapy to date of first documented radiographic and/or clinical disease progression or death from any cause. For patients removed from study for other reasons than progression or death, PFS will be censored at the date last known to be progression-free. See Section 5.9 for Replacement policy for non-evaluable patients. The %PFS6 will be calculated as the proportion of evaluable patients progression-free at 6 months. Censored patients without progression will be treated as non-progression statistically and counted in denominator toward %PFS6.

For patients who continue on treatment despite radiographic progression based upon impression of clinical benefit an/or assessment with possible pseudo-progression or a delayed response⁴⁶ (see Section 5.8), PFS will be calculated at time of first documented progression after subsequent imaging confirms progression. If subsequent imaging does not demonstrate progression, then a PFS event will not have occurred and the patient will continue with scheduled imaging assessments per protocol to determine PFS.

Re-induction and Second Course PFS (rPFS, sPFS) will be calculated in months from date of first dose of re-induction or Second Course to date of first documented radiographic and/or clinical disease progression during or after re-induction or Second Course, or death from any cause. RPFS and sPFS will be reported descriptively.

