- 4) **DOR** is defined in the subset of subjects with RECIST 1.1-measurable disease at study entry with a CR or PR as the time from first documented evidence of CR or PR until the first documented sign of disease progression or death. Re-induction and Second Course DOR (rDOR, sDOR) will be measured as the time from first documented CR or PR during or after re-induction or Second Course.
- 5) **OS** is defined as the time from the date of first dose of protocol therapy to the date of death due to any cause. Censoring will be performed using the date of last known contact for those who are alive at the time of analysis.

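### Overall survival for the re-induction and Second Course subsets keeps the study-start clock, so it includes time patients had to survive to enter them

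*Combined protocol and SAP*

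**What the plan says.** Section 8.6.2.5 is a single sentence: "Re-induction and Second Course outcomes for PFS, ORR, DOR, and OS will be measured as defined in Section 8.3". Section 8.3 treats the four outcomes as follows.

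- **ORR** (8.3.1): the re-treatment version "will be determined based upon response after first dose of re-induction or first dose of Second Course".
- **PFS** (8.3.2, item 3): the re-treatment version "will be calculated in months from date of first dose of re-induction or Second Course".
- **DOR** (8.3.2, item 4): the re-treatment version "will be measured as the time from first documented CR or PR during or after re-induction or Second Course".
- **OS** (8.3.2, item 5): one definition only, "the time from the date of first dose of protocol therapy to the date of death due to any cause". No re-treatment version appears here or elsewhere.

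Entry to the two phases is set in Section 7.1.5. Re-induction is for patients who respond or have prolonged stable disease and who "subsequently progress on single-agent pembrolizumab between 6-12 months after enrollment"; Section 4.3.4 puts this at "approximately 6-12 months (corresponding to Cycle 8-16) after enrollment". Second Course (7.1.5.2) has two routes: stopping after a confirmed complete response with at least 24 weeks of pembrolizumab, or stopping at 24 months without progression. Either must be followed by progression within 6 months of stopping.

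**The concern.** The cross-reference in 8.6.2.5 leads to an OS clock that starts before the patient could belong to the subset. Nobody can be re-induced, or start a Second Course, without first living to that point. The time from the first protocol dose to the first re-treatment dose is therefore free of deaths by construction, which is immortal time. Including it makes the reported OS longer than survival after re-treatment by exactly that interval.

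A results table built to this text would show PFS counted from the start of re-treatment next to OS counted from the start of the study, under the same subset heading. Nothing in the plan would tell the reader that the two clocks differ.

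**Working it through.** The plan states no figure for re-induction or Second Course OS, so there is none to reproduce. The check has three steps.

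**1. Can the OS definition be read as re-anchored?** No. Item 3 of 8.3.2 starts main-study PFS at the first dose of protocol therapy and re-treatment PFS at the first dose of re-induction or Second Course. The plan thus uses these as two different dates. Item 5 uses only the former, so anyone programming from 8.6.2.5 would start OS at the original first dose.

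**2. How much survival does entry require?** Inputs: 21-day cycles, so Cycle k Day 1 falls at 3 × (k − 1) weeks; 1 month = 30.44 days; entry rules from 4.3.4, 7.1.5.1 and 7.1.5.2; off-treatment scans every 8 weeks ± 28 days from 7.1.6.4.

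| Subset | Basis | Required survival |
|---|---|---|
| Re-induction | Window in months | about 6 to 12 months |
| Re-induction | Cycle 8 Day 1: 3 × 7 = 21 weeks = 147 / 30.44 | 4.8 months |
| Re-induction | Cycle 16 Day 1: 3 × 15 = 45 weeks = 315 / 30.44 | 10.4 months (10.35) |
| Second Course, complete response | 24 weeks before stopping = 168 / 30.44 | at least 5.5 months |
| Same, first scan at the early edge of its window | 24 + 4 = 28 weeks = 196 / 30.44 | about 6.4 months |
| Second Course, 24-month stop | 24 months, then progression 0 to 6 months later | about 24 to 30 months |

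As a consistency check, 35 cycles × 3 weeks = 105 weeks = 735 / 30.44 = 24.1 months, in line with the 24-month limit.

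Two approximations apply. The re-induction window is counted from enrollment and OS from first dose, so the interval on the OS clock is shorter by any gap between the two dates. Re-treatment begins at or after the progression that triggers it, which lengthens the interval slightly. If OS started at the first re-treatment dose, the required survival would be zero.

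**3. What would this do to a reported median?** This is an illustration only, because the documents give no survival after re-treatment. Let M be the true median from re-treatment and L the interval before it. If all patients were re-treated at the same month, the median under the written rule would be L + M.

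| Assumed M (months) | Re-induction, L = 6 to 12 | Second Course after 24-month stop, L = 24 to 30 |
|---|---|---|
| 3 | 9 to 15 | 27 to 33 |
| 6.7 | 12.7 to 18.7 | 30.7 to 36.7 |
| 12 | 18 to 24 | 36 to 42 |

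The added time is the same whatever M is assumed. When patients enter at different months, the median is no longer the simple sum, but every patient's value is still lengthened by his or her own L.

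**The case against.** The best defence is that immortal time misleads when it is credited to a treatment in a comparison, and the plan makes none here. Section 4.3.6.2 says only that these outcomes will be described, and 8.3.2 says the same of re-treatment PFS. There is no test, control or hypothesis. Section 8.6.2.4 plans median OS overall and by anatomic subtype, not by re-treatment. Numbers will be small: both phases need case-by-case approval, and Second Course also requires the study to be open to enrollment. All of this stands, and it limits the consequence.

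It can also be said that OS may be in 8.6.2.5 by accident. Exploratory objectives 7 and 8 (Section 3.3) list PFS, PFS6, safety, response rate and CA 19-9, but not OS. Sections 4.3.2 and 4.3.4 leave it out too. This is plausible and makes deletion as valid a remedy as a new definition. Total survival from study start is moreover a legitimate description of these patients if it is labelled as such. Neither point cures the present text, which promises OS for the re-treatment phases and supplies the wrong start date for it.

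A reader might infer that the plan sets these subsets against the 6.7-month historical median, so that re-treatment is bound to look beneficial even if it does nothing. The documents do not support that. Section 3.2 (objective 5) and Section 4.3.6.2 attach 6.7 months to the OS hypothesis for the trial as a whole, counted from the start of second-line chemotherapy. The comparison is one that a reader of the results might make, not one that the plan proposes.

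**Conclusion.** The point holds as a defect in an endpoint definition with limited reach. As written, OS for re-induction and Second Course patients includes about 6 to 12 months (4.8 to 10.4 by cycle number), at least about 5.5 months, or about 24 to 30 months of survival required for entry, depending on the route. The longest interval applies only to Second Course after the 24-month stop. The conclusion rests on the literal cross-reference and on the entry rules; the medians in the illustration are assumptions and carry no weight in it.

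The likely cause is an omission, since the other three outcomes were given phase-specific definitions. It affects one descriptive outcome in a small number of patients. It should not be read as a bias in the trial's main results: primary ORR, %PFS6 and overall-cohort OS have their own definitions and are unaffected.

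**What to change.** Choose one of two changes.

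1. Add to Section 8.3.2, item 5: re-induction OS and Second Course OS (rOS, sOS) run from the date of the first dose of re-induction or of Second Course to death from any cause, censored at last known contact for patients alive at analysis. Cite rOS and sOS in Section 8.6.2.5. This matches the start date already used for re-treatment PFS.
2. Delete OS from Section 8.6.2.5, in line with exploratory objectives 7 and 8.

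If OS from the first protocol dose is also shown for these patients, label it as total survival from study start.

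The first option costs one sentence and an amended cross-reference; the second costs one word. No new data are needed: re-treatment PFS already requires the re-treatment start dates, and survival follow-up (7.1.6.4.2) already provides vital status. The downside of the first option is that the reported survival figures become shorter.

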8.6.3 Exploratory Correlative Analyses

For exploratory endpoints, due to the limited sample size in the study, descriptive statistics with mean and 95% confidence intervals will be used. We will explore immunologic and genomic biomarkers (including PBMC immune cell subsets, TCR clonotypes frequency and diversity, tumor immune subset composition and immune infiltrates, and tumor genotype) for relationships to anatomic subtype of biliary cancer, treatment received, and to the primary and secondary efficacy endpoints. No type I error will be adjusted for multiple endpoints. For continuous variables, descriptive statistics will include the number of non-missing values, mean, standard deviation, median, min and maximum. For categorical variables, descriptive statistics will include counts and percentages per category. For comparison between subgroups, ANOVA and t-tests will be used when appropriate to determine the association of the efficacy endpoints and the specific biomarkers. For association between biomarkers, Spearman correlations will be calculated to determine the significance of the association between the biomarkers of interest. Planned analyses are described further below.

8.6.3.1 PBMC Immune Cell Subsets, TCR Clonotype Frequency and Diversity, and Other Molecular and Genetic Analyses on PBMC

Serial blood samples will be collected at timepoints in Section 6.0 – Study Flow Chart. Circulating immune cell subsets will be measured using flow cytometry as has been previously described.^{33,39} Pending funding and to be guided by clinical results of the overall study, frequency of individual TCR clonotypes and the diversity of overall TCR clonotype repertoire may be measured by next-generation sequencing as has been previously described.⁴⁰

Baseline levels of individual PBMC immune cell subset components as well as change in levels after GM-CSF induction will be explored for relationship with ORR, PFS at 6 months, and other safety and efficacy endpoints (including DOR, OS, and CA 19-9 response) to determine if there is an association using Fisher's Exact tests.

If TCR sequencing is performed on PBMC derived T cells, the frequency of TCR clonotypes with identical sequences⁴⁰ would be calculated by dividing the number of identical sequence reads by the total number of sequencing reads for that sample. TCR repertoire diversity will be calculated as the number of unique clonotypes comprising the top 25% of cumulative reads sorted by

abundance.⁴⁰ Baseline frequency and diversity as well as changes in these parameters after GM-CSF induction would be explored for relationship with PFS at 6 months as well as secondary efficacy endpoints using Fisher's Exact tests.

Exploratory analyses will be conducted to compare clonotype diversity/frequency in the safety population and Expansion Cohort after single agent pembrolizumab on Cycle 2, Day 1 before initiation of GM-CSF, with clonotype diversity/frequency after initiation of GM-CSF (intra-patient comparison), as well as to compare clonotype diversity/frequency between the safety population and Expansion Cohort (after single-agent pembrolizumab) and the efficacy population (after combination therapy) on Cycle 2, Day 1 to better understand the relative impacts and timecourse of each study drug. TCR clonotypes frequency and diversity in PBMC samples may also be compared to tumor TCR analyses if adequate sample and funding for these analyses.

Additional analyses such as immune cell gene expression profiles may also be performed depending on sample adequacy for additional testing, procurement of funding, and the main study clinical outcomes.

8.6.3.2 Tumor Immune Infiltrating Cells (TIIC) and Immune Cell Subsets in Pre-Treatment and On-Treatment Tumor Samples

The presence of tumor immune infiltrating cells (TIIC) and tumor immune cell profiles will be explored for relationship with ORR, PFS at 6 months, and other secondary efficacy endpoints (including DOR, OS, CA 19-9 response) and with tumor PD-L1 status by IHC to determine if there is a relationship using Fisher's Exact tests.

Descriptive comparisons between baseline and on-treatment or post-treatment tumor samples, or between primary and metastatic site samples and according to tumor location (e.g. liver vs. non-liver), will be performed in cases with paired samples available and between subsets in the overall study.

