8.6.2 Secondary and Exploratory Endpoints

For secondary endpoints, due to the limited sample size in the study, descriptive statistics with mean and 95% confidence intervals will be used. For continuous variables, descriptive statistics will include the number of non-missing values, mean, standard deviation, median, min and maximum. For categorical variables, descriptive statistics will include counts and percentages per category. For comparison between subgroups, ANOVA and t-tests will be used when appropriate to determine the association of the efficacy endpoints and specific biomarkers.

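### Fisher's exact test is the method named for relating continuous immune markers to DOR and OS; these exploratory analyses need a method that handles censoring

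*Combined protocol and SAP*

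**What the plan says.** Section 8.6.3.1 covers PBMC subsets: "Baseline levels of individual PBMC immune cell subset components as well as change in levels after GM-CSF induction will be explored" against ORR, PFS at 6 months and other "efficacy endpoints (including DOR, OS, and CA 19-9 response) to determine if there is an association using Fisher's Exact tests". For TCR frequency and diversity, baseline values and changes are "explored for relationship with PFS at 6 months as well as secondary efficacy endpoints using Fisher's Exact tests". Those secondary endpoints include PFS, DOR and OS under Section 8.3.2. Section 8.6.3.2 treats tumour-infiltrating immune cells and their profiles the same way, with DOR and OS in the list, "to determine if there is a relationship using Fisher's Exact tests".

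Section 8.3.2 defines OS as "the time from the date of first dose of protocol therapy to the date of death due to any cause", censored at last contact. PFS also runs from first dose and is censored. DOR is a time to event in responders, with no explicit censoring rule.

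Two other passages bear on method. Sections 8.6.2 and 8.6.3 say, in near-identical words, that for subgroup comparisons "ANOVA and t-tests will be used when appropriate to determine the association of the efficacy endpoints and specific biomarkers". Section 8.6.2.4 offers Kaplan-Meier estimates if the data support them, overall and by anatomic subtype. It does not mention PD-L1 status, although secondary objective 5 (Section 3.2) asks for median DOR, PFS and OS by PD-L1 status.

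**The concern.** Fisher's exact test works on counts in a table. To use it for a cell level, a clonotype frequency or a change score against OS, the analyst must cut the marker and cut the survival time. The plan fixes neither cut, so both would be chosen later, in a section that makes no multiplicity adjustment. Cutting discards information. A patient whose follow-up ends before the time cut either cannot be classified or is misclassified.

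The second difficulty is change after induction. The outcome clock starts at first dose, but the change is known only after two GM-CSF cycles. Some patients will have progressed or died by then, and the plan does not say how they enter the analysis.

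At stake are the correlative results that Sections 4.3.5.1 and 4.3.6.4.2 rely on to separate the contributions of the two drugs. A real association could easily be missed, and an undefined rule for unsampled patients could produce a false one.

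**Working it through.** **The plan's own figures.** The documents give no power or precision for marker-outcome analyses. The nearest figure is PFS6 power at n=40, 20% versus 40%: 78% two-sided and 87% one-sided. Exact one-sample binomial calculation gives 78.9% (reject at 14 or more of 40) and 87.1% (13 or more). These reproduce and are not in dispute.

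**Power for a continuous marker against OS.** From the documents: n=42 (Section 1.0) and historical median OS 6.7 months (Section 4.3.6.2). Assumed: exponential survival, the hazard ratio (HR) per SD of the marker, and the censoring pattern. Tests are two-sided at 5%.

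*Setting A:* censoring uniform over 12-48 months; time cut at 6 months, marker cut at its median.

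| HR per SD | Cox, nothing cut | Log-rank, marker cut | t-test of marker by 6-month status, time cut | Fisher, both cut |
|---|---|---|---|---|
| 0.7 | 55% | 38% | 32% | 14% |
| 0.6 | 82% | 61% | 57% | 25% |
| 0.5 | 96% | 84% | 80% | 44% |

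With a 12-month cut at HR 0.6, Cox has 80% and Fisher 33%. Nobody is censored before 12 months in this setting, so the loss comes from cutting alone. At HR 0.6, cutting one variable costs 21-25 points (82 − 61; 82 − 57) and cutting both costs 57 (82 − 25).

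*Setting B:* censoring uniform over 6-30 months; marker and observed time both cut at their medians; 1,500 trials per run, run three times.

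| HR per SD | Cox | Fisher |
|---|---|---|
| 1.5 | 57-59% | 12-13% |
| 1.75 | 82-85% | 23-26% |

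A 6-month cut raises Fisher to 17% and 32%.

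**Who has an event before a post-induction sample.** Induction ends at about week 6 in the Efficacy Cohort (18 patients) and week 9 in the Safety and Expansion Cohorts (9 + 15 = 24). Under exponential survival the share with an event by week w is 1 − exp(−λm), with m = 7w/30.4375 months. For PFS, λ = −ln(PFS6)/6, which is 0.153 per month at 40% and 0.268 at 20%. For OS, λ = ln 2/6.7 = 0.103. Example: PFS6 40%, week 9, m = 2.07: 1 − exp(−0.316) = 27%.

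| Outcome | Week 6 | Week 9 | Week 14 |
|---|---|---|---|
| PFS, PFS6 = 40% | 19% | 27% | 39% |
| PFS, PFS6 = 20% | 31% | 43% | 58% |
| OS, median 6.7 months | 13% | 19% | 28% |

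Week 14 is an assumed draw 8 weeks after Cycle 3 Day 1. The flow charts for the Safety and Expansion Cohorts (Sections 6.1 and 6.4) have no fixed Cycle 4 Day 1 PBMC draw; sampling after Cycle 3 is every 8 weeks ±14 days. Weighting weeks 6 and 9 by cohort size at PFS6 = 40% gives (18 × 19% + 24 × 27%)/42 = 24%.

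**Does that distort the test?** Null simulations (6,000 trials each; change unrelated to outcome; second draw at week 9 or 14) gave these type I error rates:

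- Fisher among sampled patients only: 2-4%.
- Cox from a common landmark with the clock reset: 5-6%.
- Fisher with unsampled patients counted as showing no rise: 14-44%.

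**The case against.** The strongest reply is that these are exploratory analyses on a small sample, headed as such and largely descriptive. They are partly dependent on funding, and no primary, safety or go/no-go decision rests on them. That stands and limits the weight of the point. It is also fair that the cuts and censoring in the simulations are assumed; the plan states none.

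Three stronger readings are tempting, and the documents do not support them.

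- *A reader might infer that ANOVA and t-tests are prescribed for censored times.* The sentence names neither DOR nor OS, is limited to where such tests are suitable, and can mean comparing a marker's mean between responders and non-responders or by PFS6 status. That is valid. In Setting B a t-test of the marker by 6-month status had 36% and 64% power at HR 1.5 and 1.75, against 34% and 59% for Wilcoxon.
- *A reader might infer that secondary objectives 3 to 5 depend on the faulty method.* PD-L1 is classified as positive or negative, so ORR and PFS6 by PD-L1 are binary by binary, and objective 5 asks for medians. What remains is that Section 8.6.2.4 leaves PD-L1 out.
- *A reader might infer that excluding early progressors inflates false positives and that a landmark cures this.* Restricting to sampled patients gave no inflation, and a landmark also conditions on reaching it. Inflation came only from classing unsampled patients as unchanged, which the plan neither prescribes nor excludes.

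The early-event shares also ignore the visit schedule. First restaging is at week 8 ±7 days, and the Efficacy Cohort is bled at Cycle 3 Day 1, about week 6, so scheduled imaging there normally follows the draw.

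**Conclusion.** The point holds in a limited form. Fisher's exact test is named without qualification for continuous markers against DOR and OS, and for TCR measures also against PFS through the reference to secondary endpoints. No alternative that handles censoring is named for these associations. For moderate effects with 42 patients the cost is roughly 12-25% power instead of 55-85%. That rests on exponential survival, a 6.7-month median and assumed censoring; the gap was large in every setting tried, though its exact size is not a property of the plan. Fisher remains usable for ORR and PFS6 once a marker cut-point is fixed.

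For change after induction, the defect is an undefined sampling time and an undefined rule for patients without a sample, not a demonstrated bias. For DOR, no method will have much power: at the target ORR, 0.20 × 37 gives about 7 responders. The primary ORR test is unaffected.

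**What to change.** In Sections 8.6.2 and 8.6.3:

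1. For PFS and OS, use Cox regression with continuous markers entered as continuous. For binary groups use log-rank or Kaplan-Meier. Apply the same methods to DOR, state its censoring rule, and treat the results as descriptive.
2. Add PFS, OS and DOR by PD-L1 status to Section 8.6.2.4, to match secondary objective 5.
3. For a continuous marker against ORR or PFS6, use Wilcoxon, a t-test or logistic regression. Keep Fisher for binary by binary.
4. For change after induction, name in each cohort an existing PBMC draw as the landmark. In the Efficacy Cohort this can be Cycle 3 Day 1. In the Safety and Expansion Cohorts it must be a stated draw from the 8-weekly series, with its anchor date defined. Include patients event-free at the landmark, time PFS and OS from it, stratify by GM-CSF schedule, and say that results are conditional on reaching it.
5. State that patients without a post-induction sample are not counted as showing no change.

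The cost is SAP text and slightly different code, with no new data or visits. The assays are planned in batch at study completion, so the wording can be settled before marker results exist.
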